##### Time to recovery

Time to recovery is calculated as:

date of first time WHO scale score  $\leq 3$  - study drug administration date; or date of discharge from hospital - study drug administration date, whichever occurs first.

In the case that a patient does not reach WHO scale score  $\leq 3$  criteria, the patient will be censored at EOS visit.

Additionally, time to recovery will be analyzed using an adapted derivation:

date of first time WHO scale score  $\leq 3$  – randomization date or date of discharge from hospital  $\leq 3$  – randomization date, whichever occurs first. Related output will be noted as sensitivity analysis.

Time to recovery will be analyzed based on mITT and EE Set. Sensitivity analysis for time to recovery will be analyzed based on mITT only.

Time to recovery with WHO scale score  $\leq 3$  without supplemental oxygen

Some patients were discharged from hospital while still using supplemental oxygen and so an additional sensitivity analysis will be performed to evaluate the impact for time to recovery. The following Pseudo-Code will be applied in the given order to derive time to recovery without supplemental oxygen:

1. Derive time to event 'T' as date of first time WHO scale score  $\leq 3$  - study drug administration date; or date of discharge from hospital - study drug administration date, whichever occurs first.
2. For subjects who discharged earlier than reporting an WHO scale score  $\leq 3$  apply the following checks:
  - a. If an supplemental oxygen dose of '0' is reported at day of discharge keep T.
  - b. If an supplemental oxygen dose of '0' is already reported one day prior day of discharge use T-1.
  - c. If an supplemental oxygen dose of  $>0$  is reported at day of discharge and discharge reason indicate that the subject is not on oxygen (e.g. "On Room Air" or "Weaned off O2") keep T.
  - d. If an WHO scale score  $\geq 4$  is reported at day of discharge and an WHO scale score  $\leq 3$  is reported one day after discharge use T+1.
  - e. If an WHO scale score  $\geq 4$  is reported at day of discharge and an WHO scale score  $\leq 3$  is reported two days after discharge use T+2.
  - f. If an WHO scale score  $\geq 4$  is reported at day of discharge and none of the criteria above are met use T+2.
3. In the case that a patient does not reach WHO scale score  $\leq 3$  criteria or has no discharge event, the patient will be censored at EOS visit.

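### The checks that date oxygen-free recovery (SAP 4.9.4.1, 2a to 2f) do not give coherent event times, whether checking stops at the first one met or later ones overwrite

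*SAP*

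**What the plan says.** SAP Section 4.9.4.1 adds a sensitivity analysis of time to recovery because some patients went home still on oxygen. It states: "The following Pseudo-Code will be applied in the given order to derive time to recovery without supplemental oxygen".

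- **Step 1** sets T to the time from dosing to the first WHO score of 3 or less, or to discharge, whichever comes first.
- **Step 2** adjusts T and is limited by its opening words, "For subjects who discharged earlier than reporting an WHO scale score" of 3 or less. For these patients T is the discharge time.
- **2a:** "If an supplemental oxygen dose of '0' is reported at day of discharge keep T".
- **2b:** "If an supplemental oxygen dose of '0' is already reported one day prior day of discharge use T-1".
- **2c** keeps T when a dose above 0 "is reported at day of discharge and discharge reason indicate that the subject is not on oxygen".
- **2d and 2e** apply to a WHO score of 4 or more at discharge. If a score of 3 or less follows, 2d covers the case where it "is reported one day after discharge use T+1", and 2e the case where it "is reported two days after discharge use T+2".
- **2f** gives T+2 to patients with a WHO score of 4 or more at discharge who met none of the preceding criteria.

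Neither 2a nor 2b refers to the other day's dose. The SAP does not say whether checking stops once a check is met. The revision history lists this definition as added in version 2.0 and updated in version 3.0, both times among the post-unblinding modifications.

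**The concern.** The word *already* in 2b suggests that it is meant for a patient who came off oxygen the day before discharge and stayed off. Placed after 2a, and with no condition on the discharge-day dose, it may miss that patient. It may also catch a different one: a patient off oxygen the day before who was back on it when leaving. That patient would be credited with recovery before discharge, in an analysis written to address discharge on oxygen.

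The event times feed Kaplan-Meier estimates at 5, 6, 7, 10, 14 and 28 days and Cox hazard ratios (SAP 4.9.4), in both the mITT and EE Sets. If the text allows two programs, it allows two sets of results, and the rule was written after unblinding.

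**Working it through.** The SAP states no figure for this derivation, so there is none to reproduce. The check is to run 2a-2f under both readings.

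**Inputs (SAP 4.9.4.1).** Dose the day before discharge (0, above 0, missing); dose on the discharge day (same three); discharge reason says off oxygen (yes/no); WHO 4 or more at discharge (yes/no); WHO 3 or less one day after (yes/no); WHO 3 or less two days after (yes/no). That makes 3 × 3 × 2 × 2 × 2 × 2 = 144 combinations, with 2 × 2 × 2 × 2 = 16 for each pair of doses. These count input patterns, not patients.

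**Readings.** *Stop*: the first check met fixes the time. *Overwrite*: every check runs and the last one met fixes the time. *Revised*: stop at the first check met, with 2b before 2a and requiring dose 0 on both days.

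| Dose day before / day of discharge | Stop | Overwrite | Revised |
|---|---|---|---|
| 0 / 0 (16) | T in 16 (2a) | T-1 in 10, T+1 in 2, T+2 in 4 | T-1 in 16 |
| 0 / above 0 (16) | T-1 in 16 (2b) | T-1 in 5, T in 5, T+1 in 2, T+2 in 4 | T in 12 (2c in 8, no check met in 4), T+1 in 2, T+2 in 2 |
| 0 / missing (16) | T-1 in 16 (2b) | T-1 in 10, T+1 in 2, T+2 in 4 | must be stated |
| day before not 0 (96) | as revised | differs where 2d or 2e overwrites | unchanged from stop |

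**Stop.** Any dose of 0 on the discharge day is taken by 2a, so 2b can act only when that dose is above 0 or missing. For 0 / above 0, the gap from the revised rule is:
- T-1 against T: 1 day, in 12 combinations
- T-1 against T+1: 2 days, in 2
- T-1 against T+2: 3 days, in 2

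**Overwrite.** 2b now corrects 2a for 0 / 0 unless 2d or 2e also applies. Three faults remain:
- A patient with scores of 3 or less on both days after discharge gets T+1 from 2d, then T+2 from 2e.
- A patient whose discharge reason says off oxygen gets T from 2c, then T+1 if 2d also applies.
- A patient at 0 the day before and above 0 at discharge, with WHO 4 or more, no off-oxygen reason and no later score of 3 or less, gets T-1. Meeting 2b means that 2f, which requires that nothing before it was met, cannot apply.

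**Worked example, T = 9 (illustrative).**

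| Patient | Stop | Overwrite | Revised |
|---|---|---|---|
| 0 / 0, neither 2d nor 2e met | 9 | 8 | 8 |
| 0 / above 0, WHO 4 or more, no off-oxygen reason, no later score of 3 or less | 8 | 8 | 11 |
| 0 / above 0, WHO 4 or more, no off-oxygen reason, 3 or less the next day only | 8 | 10 | 10 |
| 0 / above 0, off-oxygen reason, no later score of 3 or less | 8 | 9 | 9 |

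**Effect on a landmark.** Thirty patients randomized 1:1:1 give 30 / 3 = 10 per arm. Without earlier censoring, one patient moved across a landmark changes that arm's estimate by 1 / 10 = 10 percentage points. For example, with T = 7, T-1 = 6 counts at the 6- and 7-day landmarks; T+2 = 9 counts only from the 10-day landmark.

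**The case against.** **Overwriting may be what was intended.** Running checks in order also describes successive IF statements. The condition inside 2f would be redundant if checking stopped at the first check met, and *already* can be read as 2b refining 2a. This stands in part: a reader might infer that patients who stay off oxygen are simply dated a day late, but that holds only under stopping. Overwriting does not repair the list, because 2c, 2d and 2e make sense as a sequence only if checking stops.

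**The early dating is not universal.** A reader might infer that a patient back on oxygen gets T-1 whichever way the list is run. Under overwriting, T-1 survives in only 5 of 16 combinations. Nor is the error open-ended: 2c recognises patients with a recorded dose above 0 who left off oxygen, and the SAP's own latest time is T+2, so the gap against its rules is at most 3 days.

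**One oxygen-free day may be enough.** Step 1 uses the first WHO score of 3 or less and does not ask that it last. On that logic T-1 for a patient back on oxygen is defensible. This also stands in part, but the SAP does not say so, and stopping would still date that patient ahead of one who stayed off.

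**Few patients can be affected.** Hospitalized without oxygen is WHO score 3, so a patient off oxygen at a scheduled score normally never enters step 2. A reader might tie the problem to every discharge on a day without a scheduled score. The day before matters too: discharges on Days 8 and 11 follow scheduled scores on Days 7 and 10. A score is also scheduled at discharge itself. This stands.

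**Conclusion.** The point holds as a defect in the derivation. Under stopping, 2b misses the patients it appears meant for and gives an earlier time to patients whose discharge-day dose is above 0 or missing. Those back on oxygen are dated 1 to 3 days before the time that the revised rule gives. Under overwriting, 2d and 2e displace earlier results, and one clear case of discharge on oxygen still gets T-1 instead of T+2. Two programmers could follow the text and produce different event times.

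The size is limited. The documents give no count of affected patients, and entry to step 2 makes a small number likely. The checks move event times by days and do not change whether a patient has an event, so the 10-point figure applies only when a patient crosses a landmark. This is a sensitivity analysis of a secondary endpoint in a study without a power calculation, and its p-values are exploratory. The primary safety endpoint is untouched.

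Because the rule was written after unblinding, a reader might infer that it favours ATYR1923. The documents do not support that: they give no affected patients by arm and no direction of effect between arms.

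The verdict assumes that 2b is meant for patients who stayed off oxygen, which its wording suggests but does not state.

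**What to change.** In SAP 4.9.4.1, step 2:

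1. State that the first check met applies and that checking then stops.
2. Put 2b before 2a and restrict it to dose 0 reported on both the day before and the day of discharge: use T-1.
3. Send patients with a dose above 0 on the discharge day to 2c-2f.
4. State the result when the discharge-day dose is missing.
5. State the result when no check is met: dose above 0, no off-oxygen reason, and no WHO score of 4 or more recorded at discharge. Reordering alone leaves such a patient at T.

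If the sponsor wants any first oxygen-free day to count, in line with the first-score definition in step 1, it should say so and still put 2b before 2a.

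The cost is a few lines of SAP text, a small program change and a rerun of this analysis in the mITT and EE Sets. No new data are needed. The change should be labelled as made after unblinding, and the report should give the number of patients, by arm, whose event time it alters.

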## 6.2 WHO Ordinal Scale for Clinical Improvement

Patient State	Descriptor	Score
Uninfected	No clinical or virological evidence of infection	0
Ambulatory	No limitation of activities	1
	Limitation of activities	2
Hospitalized Mild disease	Hospitalized, no oxygen therapy	3
	Oxygen by mask or nasal prongs	4
Hospitalized Severe Disease	Non-invasive ventilation or high-flow oxygen	5
	Intubation and mechanical ventilation	6
	Ventilation + additional organ support – pressors, RRT, ECMO	7
Dead	Death	8

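### The sensitivity analysis of recovery without oxygen can date a patient discharged on oxygen as oxygen-free from a WHO score that does not record oxygen

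*SAP*

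**What the plan says.** SAP 4.9.4.1 (Time to recovery) gives the reason for the extra analysis: "Some patients were discharged from hospital while still using supplemental oxygen and so an additional sensitivity analysis will be performed". The SAP revision history lists it among the post-unblinding changes of versions 2.0 and 3.0.

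Step 1 sets T at the first WHO score of 3 or less, or at discharge, whichever is earlier. Step 2 then applies checks to a limited group: "For subjects who discharged earlier than reporting an WHO scale score" of 3 or less. Within step 2:

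- Rules 2a and 2b use a recorded oxygen dose of zero on the day of discharge or the day before.
- Rule 2c keeps T when a dose above zero is recorded but the discharge reason shows that the patient is off oxygen.
- Rules 2d and 2e start from a score of 4 or more at discharge. If a score of 3 or less "is reported one day after discharge use T+1"; if it "is reported two days after discharge use T+2".
- Rule 2f is the default: a score of 4 or more that "is reported at day of discharge and none of the criteria above are met use T+2".

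In the scale in SAP 6.2, score 3 is "Hospitalized, no oxygen therapy" and score 4 is oxygen by mask or prongs, also an in-hospital state. Scores 1 and 2 are ambulatory states separated by limitation of activities. Score 0 is the uninfected state. None of 0, 1 or 2 mentions oxygen, and the scale has no category for oxygen at home.

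**The concern.** The patients this analysis is meant to examine are those who left hospital on oxygen. For them, a fall from 4 to 2 can come from leaving hospital alone. A score of 3 or less shows absence of oxygen only when it is an in-hospital 3, and a patient at home is not in that category.

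The derivation nevertheless relies on the score in two places. A score of 0 to 2 on the day of discharge means that the patient was not discharged before reaching 3 or less, so step 2 is skipped and T is kept whatever the oxygen record shows. Rules 2d and 2e move the date by one or two days on a post-discharge score without consulting oxygen data.

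At stake is whether the analysis can show an effect of discharge on oxygen. A patient dated too early counts as recovered in the Kaplan-Meier estimates that SAP 4.9.4 requests at 5, 6, 7, 10, 14 and 28 days, on both the mITT and EE Sets.

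**Working it through.** The plan states no figure for this point, so the check is to run the rules on a case.

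**Inputs.** Rules: SAP 4.9.4.1. Scale: SAP 6.2. Time is event date minus dosing date, so Day d corresponds to time d − 1. Contacts after discharge: Day 7 and Day 14 where applicable, then Days 28 and 60 (Protocol Table 1, footnote 1, and synopsis). Arm size: 30 patients randomized 1:1:1, so about 30/3 = 10 per arm (SAP 3.1.4).

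**Assumed patient.** Discharged on Day 6 with an oxygen dose above zero on that day and the day before, a discharge reason that does not indicate being off oxygen, and no earlier score of 3 or less. Oxygen stops on Day 20. Then T = 6 − 1 = 5 and the oxygen-free time is 20 − 1 = 19. Rules 2a to 2c do not apply.

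| WHO scores | Route | Result | Days early |
|---|---|---|---|
| 2 on day of discharge | step 1 only | 5 | 19 − 5 = 14 |
| 4 at discharge, 2 on Day 7 | 2d | 5 + 1 = 6 | 19 − 6 = 13 |
| 4 at discharge, 2 on Day 8 | 2e | 5 + 2 = 7 | 19 − 7 = 12 |
| 4 at discharge, next score on Day 14 | 2f | 5 + 2 = 7 | 12 |
| 4 at discharge and 4 until oxygen stops | 2f | 5 + 2 = 7 | 12 |

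The results are the same whether the first or the last matching rule governs. For a general stop time S, the result is early by S − T, S − T − 1 or S − T − 2. The gap therefore grows one for one with time on home oxygen, while the derivation adds at most two days. The last two rows show that removing 2d and 2e alone would not help, because 2f returns 7.

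**How often the score-based routes can apply.**

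- *Day-of-discharge score.* Protocol 8.3.2 has the score determined between 06:00 and 10:00, or per local practice, and the one closest to 08:00 recorded. A patient still on the ward on mask or prongs at that hour scores 4. A score of 0 to 2 while on oxygen needs a later score, the local-practice exception or a misclassification.
- *Rule 2d.* On nominal days, a contact falls one day after discharge only for discharge on Day 7 − 1 = 6, 14 − 1 = 13, 28 − 1 = 27 or 60 − 1 = 59.
- *Rule 2e.* Likewise only for discharge on Day 5, 12, 26 or 58.
- Calls made off the nominal day could add cases, because SAP 4.2 bases time-to-event calculations on actual dates.

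**Effect of one patient.** With about 10 per arm, one patient dated at 5, 6 or 7 instead of 19 moves the crude recovered proportion at 7, 10 and 14 days by 1/10, or 10 percentage points. At 28 days there is no difference in this example.

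**The case against.** The strongest reply is that the score-based routes are narrow. The morning window makes the first uncommon, and the call schedule limits the second to a few discharge days. That stands. So does the point that the documents do not say how sites score a discharged patient on oxygen. Some may enter 4, and the patient then falls to rule 2f.

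A reader might infer that every patient discharged on oxygen is misdated by a WHO score. If 10% to 30% of about 10 patients per arm went home on oxygen (an assumption), that would be 1 to 3 per arm. The documents do not support assigning all of them to these two routes: most would reach 2f, and some could be resolved by 2c. A reader might also infer that the whole analysis must look reassuring. That goes too far, because rules 2a to 2c do use the oxygen dose or the discharge reason.

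Home oxygen is also not invisible elsewhere. The secondary endpoint on duration of supplemental oxygen, in the same SAP section, uses stop dates and sums all periods. That reports it descriptively but does not correct the recovery date, and the two analyses could imply different oxygen-free dates for one patient.

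Finally, rule 2c implies that the oxygen record can overstate use on the day of discharge. A remedy that relied on stop dates alone could delay or censor patients already weaned. This is right, and the remedy has to keep 2c.

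**Conclusion.** The point holds as a defect of the derivation with limited reach. A patient discharged on oxygen can be dated as oxygen-free from a score that carries no oxygen information, at T, T+1 or T+2. The number dated this way is not given, is probably small and could be zero. Together with rule 2f, the wider consequence is that where these rules apply the analysis adds no more than two days, so for those patients it cannot show how much continuing oxygen delays recovery.

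The example's 12 to 14 days rest on an assumed stop on Day 20; only the two-day ceiling comes from the text. This is a sensitivity analysis in a study without a power calculation and with exploratory p-values (SAP 3.1.4 and 4.9.2). The primary endpoint, incidence of treatment-emergent adverse events, is unaffected. The correction is worth making because it is cheap and the analysis has this one purpose.

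**What to change.** Change the entry condition of step 2 and replace rules 2d, 2e and 2f together:

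- For every patient with an oxygen record ongoing at discharge and no discharge-reason evidence of being off oxygen, whatever the WHO score, take the recovery date as the recorded oxygen stop date. Censor at last contact if no stop is recorded.
- Keep rule 2c.
- Accept a WHO score as evidence of being oxygen-free only if it is an in-hospital 3, or if no oxygen record is ongoing on that date.
- State which clause governs for a patient with an in-hospital 3 who is back on oxygen at discharge, since the first and third would otherwise conflict.

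The data are already planned. Oxygen is captured as a concomitant medication (Protocol Table 1, footnote 17, and sections 8.3.2 and 8.6.4), concomitant medications are scheduled through outpatient follow-up, and the SAP's oxygen-duration endpoint already uses stop dates. The cost is SAP wording and reprogramming. The downsides are some later or censored times and reliance on the completeness of oxygen stop dates after discharge. Because the existing rules were added after unblinding, the revised derivation should be labelled as post hoc too.

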### 4.2 General Presentation Considerations

**Baseline:** the last available pre-treatment assessment, unless otherwise specify. All assessments should have time collected. If time is not collected and date of assessment is the same as study drug administration date then assessment will be assumed to be collected prior to treatment unless schedule of assessments and protocol indicate planned collection is always after dosing.

For baseline of oxygen use, total oxygen use in 24 hours before drug administration date.

**Day-of-Discharge (DoD):** day when patient is discharged from the hospital.

**Date of discharge:** date patient is discharged from the hospital.

**Early Termination (ET):** day when patient withdraws from the study before completion.

**End-of-Study (EOS):** the EOS assessment is at Day 60 for patients who complete the study.

**End of study date:** date of EOS assessment (Day 60) if patient completes the study or date of early withdrawal if patient discontinues early, or date of death.

**Study Day:** <Assessment Date> - study drug administration date + 1 if <Assessment Date> is on or after study drug administration date. <Assessment Date> - study drug administration date, if <Assessment Date> is before study drug administration date.

Durations are generally calculated as the stop date - start date +1, if not otherwise stated.

For elapsed time (eg, time since the initial diagnosis) is calculated as reference date - event date.

If more than one laboratory value is available for a given study day, the last valid observation will be used in summaries, unless otherwise stated. If it is not possible to determine which is the last measurement due to missing times, then the average of all measurements for that study day will be used as the value for that study day. All observations will be presented in listings.

Laboratory data will be presented in standard units.

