## **4.3 Missing Data**

### **4.3.1 Imputation of Non-Date Missing Data**

Missing data occurs when any requested data is not provided, leading to blank fields on the collection instrument. These data will be indicated by the use of a “blank” in subject listing displays. Answers such as “Not applicable” and “Not evaluable” are not considered to be missing data and should be displayed as such.

Subjects with the designation of treatment relationship for AEs and SAEs missing will have the worst realistic case assumed to impute the relationship: if relationship is missing and the AE started on or after study drug administration it will be assumed to be “related” (worst case). If the AE with missing relationship started before study drug administration (eg, during Screening Period), it will be considered as “not related” (realistic case). Missing Severity will be assumed to be “Life-threatening” (worst case). In listings these imputed relationships and causalities will be flagged.

For variables which determine the proportion of events, all subjects in the respective analysis set will be included in the denominator when calculating the percentages irrespective of whether their outcome may be missing.

Handling of complete or partial missing dates for Adverse Events or reported Concomitant Medication will be given in the following Section.

All other missing data will not be imputed.

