**Table 4 Partial Date Imputation Rules for AEs and Medications**

Date	Missing Element	Rule
Start Date	day, month, and year	Do not impute completely missing start dates
	day, month only	Set to January 1 st of the year the event started.
	day only	Set start date to the 1 st of the month the event started.
End Date	day, month, and year	No imputation for completely missing end dates; report the event as ongoing if not already documented as 'ongoing'
	day, month only	If the partial end date contains year only, set end date to December 31 st or last study visit, whichever occurs first.
	day only	If the partial end date contains month and year, set the end date to the last day of the end month or last study visit, whichever occurs first.

Thus, AEs will be assumed to be treatment-emergent, unless there is clear evidence to suggest that the AE started prior to treatment.

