Time to recovery with WHO Scale score  $\leq 3$  and without supplemental oxygen will be analyzed based on mITT and EE Set.

*Proportion of patients achieving recovery by Day 14 and by Day 28*

Number and percentage of patients achieving recovery (WHO scale score  $\leq 3$  or discharge from hospital, whichever occurs first) by Day 14 and by Day 28 will be presented.

*Duration of supplemental oxygen (O2) requirement :*

The number of days with supplemental oxygen (O2) will be calculated as:

stop date of supplemental oxygen – start date of supplemental oxygen +1; if supplemental oxygen started after study drug administration; otherwise supplemental oxygen – date of study drug administration +1.

If there are multiple periods of supplemental oxygen (O2), total days will be the sum of each period. Patients who die or withdraw from the study with ongoing supplemental oxygen at the last contact date, days will be (earliest of [date of death, EOS date] – start date of supplemental oxygen +1). Standard descriptive statistics (mean, SD, median, minimum, maximum) will be used. Standard descriptive statistics will also be presented for mITT Set excluding withdrawals and deaths.

Days of supplemental oxygen (O2) up to Day 14 will be used as a sensitivity analysis. Days will be calculated as below:

- For patients who Die or Withdraw before Day 14, their total will be factored-up to an equivalent 14 day period. For example, if a patient withdraws on Day 5 having already received 3 days of supplemental oxygen between Day 1 and Day 5, then their endpoint value will be 8.4 days i.e.  $(3/5)*14$  .
- For patients who do not withdraw or die before Day 14, count the actual days on supplemental oxygen (O2) up to Day 14.

*Number of days with fever (temperature  $>100.4^{\circ}\text{F}$  [ $38.0^{\circ}\text{C}$ ]):*

The Number of days with fever are calculated as:

stop date of fever – start date of fever +1, if fever started after study drug administration; otherwise stop date of fever – date of study drug administration +1.

If there are multiple periods of fever, Total days will be the sum of each period. Standard descriptive statistics (mean, SD, median, minimum, maximum) will be used. Standard descriptive statistics will also be presented for mITT Set excluding withdrawals and deaths.

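### The SAP gives no end date for oxygen still in use in a patient who completes Day 60, so that patient's oxygen duration is missing or understated if the rules are followed literally

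*SAP*

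**What the plan says.** Duration of supplemental oxygen is a listed secondary endpoint (Protocol 3.2, SAP 3.4.2). SAP 4.9.4.1 derives it as "stop date of supplemental oxygen – start date of supplemental oxygen +1; if supplemental oxygen started after study drug administration"; for oxygen already running at dosing, the count begins at the dosing date instead. With several periods, "total days will be the sum of each period". The result is summarised descriptively in the mITT Set, and again without deaths and withdrawals.

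One sentence deals with oxygen that has not stopped. It opens "Patients who die or withdraw from the study with ongoing supplemental oxygen at the last contact date, days will be" and gives the value as "earliest of [date of death, EOS date] – start date of supplemental oxygen +1". Nothing is said about a patient who completes the study with oxygen ongoing.

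The EOS date is nonetheless defined for such a patient. SAP 4.2 gives it as "date of EOS assessment (Day 60) if patient completes the study or date of early withdrawal if patient discontinues early, or date of death".

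On missing dates, Table 4 in SAP 4.3.2, which covers medications, says "No imputation for completely missing end dates; report the event as ongoing". SAP 4.3.1 closes with "All other missing data will not be imputed". Supplemental oxygen is recorded as a concomitant medication (Protocol Table 1, footnote 17).

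**The concern.** The rule for unfinished oxygen names two groups and leaves out a third that the SAP itself recognises: the EOS definition in SAP 4.2 separates completion, early withdrawal and death, and the disposition summary in SAP 4.6.1 counts completers apart from early withdrawals. A completer still on oxygen at Day 60 would have one of the longest durations in the trial, and is the patient for whom the formula has no stop date.

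The situation is plausible. In adding an oxygen-free version of time to recovery, the SAP records that "Some patients were discharged from hospital while still using supplemental oxygen". The duration endpoint received no matching provision.

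With about 10 patients per arm, a single missing or shortened value can move an arm mean by several days.

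**Working it through.** The plan states no figure for this endpoint, so there is nothing to reproduce. The check traces the rule and then sizes one affected patient.

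**Tracing a completer with oxygen ongoing at Day 60**

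1. The main formula in SAP 4.9.4.1 needs a stop date. An ongoing record has none.
2. The ongoing-oxygen sentence applies to deaths and withdrawals. The patient is neither.
3. Table 4 leaves a completely missing medication end date unimputed and reports the record as ongoing. SAP 4.3.2 also restricts imputed dates to assigning study periods, classifying medications as prior or concomitant, and deciding treatment emergence. Durations are not among these uses.
4. SAP 4.3.1 imputes nothing further.
5. Result: one open record gives no value. If earlier periods are closed, summing the closed ones gives a total that is too low.

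The summary without deaths and withdrawals does not help, because the ongoing-oxygen sentence reaches nobody in it.

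Elsewhere the SAP does close this gap. Time to discharge censors patients still in hospital at EOS (4.9.4.1), and intubation days run to extubation or EOS, whichever is earlier (4.9.4.2).

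**Size, one affected patient, no value**

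Inputs: 30 patients allocated 1:1:1 (SAP 3.1.4), so n = 10 per arm and n = 20 for the two active arms pooled. Oxygen from Day 1 through an EOS assessment on Day 60 counts 60 − 1 + 1 = 60 days. The mean of the other patients, m, is not in the documents; 5 to 15 days is assumed.

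Mean with the patient omitted: m. Mean with the patient counted: ((n − 1) × m + 60) / n. Difference: (60 − m) / n.

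| n | m (omitted) | Patient counted | Difference |
|---|---|---|---|
| 10 | 5 | (9×5 + 60)/10 = 10.5 | 5.5 |
| 10 | 10 | (9×10 + 60)/10 = 15.0 | 5.0 |
| 10 | 15 | (9×15 + 60)/10 = 19.5 | 4.5 |
| 20 | 5 | (19×5 + 60)/20 = 7.75 | 2.75 |
| 20 | 10 | (19×10 + 60)/20 = 12.5 | 2.5 |
| 20 | 15 | (19×15 + 60)/20 = 17.25 | 2.25 |

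**Size, one affected patient, partial value**

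Illustration: oxygen closed on Days 1 to 10 and open from Day 11. Closed records alone give 10 days; counted to EOS the total is 10 + (60 − 11 + 1) = 60. The 50 lost days lower the mean of an arm of 10 by 50/10 = 5.0 days, and the patient still counts in n.

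**A second inconsistency in the same rule**

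The main formula starts no earlier than dosing. The death and withdrawal formula starts at oxygen start, which can precede dosing. Extending the EOS cut to completers without changing this would leave two clocks in one endpoint.

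**The case against.** The best reply is that the SAP is silent about these patients and does not exclude them. The EOS date exists for completers, the ongoing-oxygen formula already uses it, and EOS is the cut-off for the other endpoints. A record marked ongoing is arguably a known status and not missing data, so the no-imputation rules need not bite. A sensible programmer would count to Day 60. That is fair as a prediction, but the choice would be undocumented: the sentence that could have authorised it names only deaths and withdrawals.

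The consequences are also limited. The endpoint has descriptive statistics and no test, in a study without a power calculation. The median is reported as well as the mean. SAP 4.2 requires the number of observations, so a wholly omitted patient would show as n = 9, and SAP 4.9.4.2 lists all oxygen use by patient. The Day 14 sensitivity analysis counts actual days for anyone who has not died or withdrawn by then. All of this stands and limits the seriousness. It does not repair the main analysis: an understated total would not show in n, and the Day 14 analysis says nothing about need after Day 14.

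A reader might go on to infer that patients with no oxygen or fever after dosing are lost too. The documents do not support that: the total is a sum over periods, and a sum over no periods is naturally 0. An explicit zero would be helpful detail, but its absence is not a fault of the same kind.

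**Conclusion.** The gap is real and should be closed. Followed literally, the SAP gives a Day 60 completer on ongoing oxygen either no duration or too low a total. Losing one such patient understates the mean of an arm of 10 by about 4.5 to 5.5 days, or the pooled active mean by 2.25 to 2.75 days. Those figures assume continuous oxygen from Day 1 to Day 60 and an average of 5 to 15 days in the other patients; neither comes from the documents.

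Two stronger conclusions are tempting and not supported. A reader might take discharge on oxygen to mean oxygen at Day 60, but the SAP reports only the former and gives no count, so the number affected may be zero. A reader might also infer that the treatment comparison is tilted in a known direction. That would depend on which arm holds the affected patients, and the documents do not say.

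**What to change.** In SAP 4.9.4.1, replace the ongoing-oxygen sentence with a rule for every patient whose oxygen is ongoing at last contact, completers included:

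- days in the ongoing period = earliest of (date of death, EOS date) − latest of (study drug administration date, oxygen start date) + 1;
- use this same clock for deaths and withdrawals, so that days before dosing count for nobody;
- add the result to any earlier closed periods;
- report by arm how many durations were cut off at EOS, since those values are lower bounds.

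The cost is one revised sentence, one extra table row and a rerun of the duration tables. No new data are needed: oxygen is already recorded as a concomitant medication, and concomitant medications are collected at the follow-up visits. SAP versions 2.0 and 3.0 already carry post-unblinding modifications, so this change should be labelled as another, or as post hoc under SAP 3.2 if it comes after database lock.
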